7.1.3. Initial Approach

Following diagnosis, the treating clinician, ideally along with a member of the department research team, should make the initial approach to the patient during the clinic appointment. The clinician will explain that the patient may be eligible for the trial, as well as the basic premise of the trial. If the patient is interested in knowing more about the trial, they will be given the patient information sheet (PIS) to take away and advised to read and discuss with family members, friends or their GP before making a decision. If it is not possible to approach the patient during a clinic appointment the appropriate PIS(s) can be sent in the post. However, this approach to patient should only take place after a patient has been told of their diagnosis by their clinician. Patients will be given the opportunity to ask more questions and discuss the trial further at their pre-operative visit, prior to consenting. Patients must be given a minimum of 24 hours between the initial approach and consenting to allow sufficient time for them to consider whether the participating in the trial is right for them.

7.2. Consent

After allowing a minimum of 24 hours to consider their involvement in the trial, the trial can be rediscussed with the patient. If the patient is willing to participate and their eligibility criteria have not changed, written informed consent for the trial may be given. Consent will be taken by the PI, or, where delegated by the PI, other appropriately trained (clinical and non-clinical) site staff. A surgical consent form, separate from the trial, will also be completed by the patient as part of standard of care procedures.

The original signed consent form must be filed in the investigator site file (ISF), a copy must also be filed in the patient's medical records, and another copy given to the patient for their records. Copies of the version of PIS given to the patient must be filed in the ISF and the patient's medical notes. Patients should be asked at every follow up assessment if they would like to continue in the trial. This discussion and response should be recorded in the patient's clinical records.

In the case of protocol amendments or if information becomes available which may affect participants' willingness to continue in the trial, it may be necessary to re-consent participants on an updated consent form after necessary regulatory approvals are obtained. If more than 28 days lapses between consent and surgery, patients will need to be reconsented and eligibility reconfirmed. If a child who was consented into the trial by a parent/carer turns 16 during their time in the trial, they will need to be reconsented using the 16+ consent form.

7.3. Randomisation

Confirmation of eligibility will be taken by a clinician delegated to the trial. Confirmation of eligibility must be documented in the patient's medical records. Only after eligibility is confirmed can the patient be randomised into one of the trial arms. If the patient has not met all the eligibility criteria, they cannot continue in the trial and will be entered as 'withdrawn' on the database.

Eligible participants will be randomised in a 1:1 ratio to standard surgery vs FGS using ICG, stratified by acceptable close/positive margin, sarcoma sub-type and treating centre. Randomisation will be conducted by a delegated and trained member of the research team at each site using the Sealed Envelope system, which is a central, secure, 24-hour web-based randomisation system with concealed allocation. Randomisation should take place as soon as possible after consent and no more than one week after a participant has consented. The allocation sequence will be computer-generated, using a permuted block design. Block size will not be disclosed, to ensure concealment.

For those patients who have been randomised to having FGS using ICG, clinicians should document in the medical notes the dosage requirement of ICG as 1mg/kg. This will ensure the prescribing doctor on the day of ICG administration, who may not be delegated to the trial, prescribes the correct dosage. Under dosing a patient is likely to happen if dosage is done using the SmPC as a guide. **Under dosing a patient could mean the tumour does not adequately fluoresce.**

Randomisation system URL: https://www.sealedenvelope.com/access/

This system is available 24 hours a day, seven days a week. If the online system is not accessible at the site, NCTU can liaise with Sealed Envelope Support to investigate the cause. Site staff should contact NCTU Database Support during normal working hours:

Email: [contact] [contact]

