Population	intermediate to high-grade bone or	soft tissue sarcoma suitable for		
	curative resection.			
Planned Sample Size	Total n=500 (FGS with ICG n=250, S	tandard Care n=250)		
Planned Number of	Up to 20			
Sites				
Intervention Duration	12–24-hour time period between t	ne administration of intravenous		
	(IV) ICG and the start of the resection.			
Follow Up Duration	Patients will be followed up for 12 months following the procedure,			
	with the option of an additional time point at 5 years if further funding			
	is secured.			
Planned Trial Period	58 months (7 months setup, 30 mo	nths of recruitment, 3 months		
	surgical delay, 12 months follow up	, 6 months final		
	report/dissemination)			
	Objectives Outcome Measures			
Primary	To determine whether FGS using	The UPM rate, defined as the		
	ICG reduces the UPM rate	percentage of patients with an		
	compared to the current standard	unexpected positive margin, will		
	of care (SoC).	be compared between the two		
	treatment arms.			
Secondary	Complications	Rates of intra- and postoperative		
	complications as recorded in the			
	clinical notes.			
	Length of index operation Difference in length of operation			
	in minutes.			

TRIAL SUMMARY

	Length of inpatient stay	Difference in length of inpatient stay in days.			
	Perceived impact of intervention in surgical decision making	The percentage of operations in which the surgeon stated FGS changed their planned resection.			
	Local recurrence (LR) rate	The difference in rate of local recurrence at 12 months.			
	Regional/distal recurrence rate	The difference in rate of regional/distal recurrence at 12 months.			
	Overall survival (OS) rate	The difference in rate of overall survival at 12 months.			
	Identify rates of adjuvant and neo-adjuvant therapies	Rates of adjuvant and neo- adjuvant therapies as per clinical notes.			
	Quality of life (QoL) measurements	The difference in scores on EQ- 5D-5L/EQ-5D-Y.			
	Recovery following resection	The difference in scores on the Toronto extremity salvage score (TESS)/ Paediatric Toronto extremity salvage score (pTESS)			
Exploratory Objectives	To determine the role of ICG in the pathological margin assessment of resected sarcoma specimens	Fluorescence microscopy to assess extracellular and cellular ICG spatial orientation in tumour tissue versus surrounding normal tissues			

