3.1.2. Secondary Objective(s)

To determine the effect of FGS using ICG compared to the SoC over a 12-month period on the following areas:

- o Complications
- Length of index operation
- Length of inpatient stay

- Perceived impact of the intervention on surgical decision and change in surgeon preference throughout the trial
- Local recurrence
- Regional/distal recurrence
- Rates of adjuvant and neo-adjuvant therapies.
- Overall survival
- Quality of life (QoL)
- Recovery following resection

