3.3.2. Secondary Outcomes

The length of index operation and type and frequency of adjuvant and neo-adjuvant therapies will be compared between FGS and SoC groups on the day of operation. Local/regional/distal recurrence and difference in overall survival will be compared between the two groups at the 12-month time point. The number of complications and length of hospital inpatient stay will be compared between the two groups at day of operation and at 1-, 6- and 12-month follow-up time points. EQ-5D-5L/EQ-5D-Y scores and TESS/pTESS scores we be compared between the two groups at every follow up time point.

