7.1.2. Screening

All patients discussed at the MDT with a new histologically confirmed diagnosis of intermediate to high grade sarcoma should be screened for eligibility. Because the time between diagnosis and surgery tends to be relatively short (i.e., a couple of weeks), it is important that screening is achieved in a timely manner so that patients can be approached, given time to consider the trial and then consented to the trial prior to their surgery.

An electronic screening log on the Sealed Envelope Red Pill database will capture pseudonymised screening data including the following:

• Date of screening

SarcoSIGHT Protocol version 5.0 dated 25 June 2024

- Age of patient at screening
- o Sex of patient at birth
- o Histologically confirmed diagnosis of intermediate to high grade sarcoma
- o Tumour Amenable to curative surgical resection
- Patient interest in taking part (Yes/ No)
 - If no, reason given
- Patient information sheet (PIS)given
- o Date PIS given

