8.3. Concomitant Medications & Therapies

Participation in another interventional clinical trial in the 30 days preceding surgery are permitted.

All neo-adjuvant treatment regimens are permitted.

The class of concomitant medications that need to be reported are:

- o Tyrosine kinase inhibitors
- o Immunotherapy

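### Randomisation and baseline are timed from consent with no limit on the interval to resection, and neo-adjuvant therapy is treated as an effect of FGS

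*Protocol*

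**What the plan says.** Section 7.3 times randomisation from consent alone: "Randomisation should take place as soon as possible after consent and no more than one week after a participant has consented". The schedule in 7.7 puts consent, staging, tumour details, EQ-5D, TESS and randomisation in the same pre-operative column. One of the stratification factors is the expected acceptable close/positive margin.

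The protocol describes the time to surgery in several places:

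- Section 7.1.2 says that "the time between diagnosis and surgery tends to be relatively short (i.e., a couple of weeks".
- Section 7.1.3 has the patient discuss the trial again at the pre-operative visit before consenting.
- The planned trial period in the Trial Summary has a 3-month item between recruitment and follow-up ("surgical delay, 12 months follow up"), not explained further.
- Section 7.2 foresees longer gaps: "If more than 28 days lapses between consent and surgery, patients will need to be reconsented and eligibility reconfirmed".

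On treatment before surgery, 8.3 states: "All neo-adjuvant treatment regimens are permitted". Section 3.1.2 lists "Rates of adjuvant and neo-adjuvant therapies" among the areas on which the effect of FGS is to be determined. Section 3.3.2 says that the "type and frequency of adjuvant and neo-adjuvant therapies will be compared between FGS and SoC groups on the day of operation". Under 8.1.2, FGS begins with the ICG injection 12-24 hours before the procedure.

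**The concern.** A limit counted from consent does not limit the time to surgery. If surgery is delayed after consent, several things follow in an open-label trial.

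- Patient and operating team know the arm (7.4) for the whole wait.
- Re-consent after 28 days takes place with the arm known. A patient who then leaves before the intervention is replaced (7.8). Replacement restores the count but not the comparability of the randomised groups, and it sits uneasily with the intention-to-treat analysis in 10.2.1.
- The margin stratum, tumour size, stage, EQ-5D and TESS are not retaken. If treatment is given during the wait, they may no longer describe the patient who reaches theatre.

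Two planning statements depend on a short interval. Section 10.2.1 expects few missing outcomes because the margin is known soon after randomisation. Section 10.3 justifies its small dropout allowance in the same way. For delayed patients both premises are weaker.

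The classification of neo-adjuvant therapy is a separate fault that does not depend on the timing. A between-arm difference in therapy given before FGS begins would be reported under an objective about the effect of FGS.

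**Working it through.** **1. Timeline.** The Trial Summary gives 7 + 30 + 3 + 12 + 6 = 58 months, which reproduces the stated total. Follow-up is counted from surgery ("Patients will be followed up for 12 months following the procedure"), so the 3 months lie between the end of recruitment and the last operation.

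**2. Length of the gap.** Three months is 3 × 365.25/12 = 91.3 days.

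- Against the re-consent trigger: 91.3/28 = 3.3 times as long.
- Against a couple of weeks, read as 14 days: 91.3/14 = 6.5 times as long.
- With randomisation up to 7 days after consent, 91.3 − 7 = 84.3. At the outer edge of the budget the arm is known about 84 to 91 days before resection.

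**3. Sequence for a delayed patient.** Consent is on day 0 and randomisation by day 7. After day 28 come re-consent and an eligibility check, with the arm known. No new baseline and no updated stratum are required. A withdrawal before intervention is replaced.

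**4. Possible loss before surgery.** The allowance is 500 − 480 = 20 patients, or 20/500 = 4%, and 480/0.96 = 500 reproduces the planned total. The protocol gives neither the delayed share f nor the loss q within it, so both are assumptions:

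- f = 20-40%, q = 2-8%: from 500 × 0.20 × 0.02 = 2 to 500 × 0.40 × 0.08 = 16 patients, inside the allowance of 20.
- f = 20-60%, q = 5-20%: from 0.20 × 0.05 = 1% to 0.60 × 0.20 = 12% overall, which can exceed 4%.

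**5. Power.** Inputs are 13.8% against 5% (10.3) and the one-sided threshold 0.0227 (10.2.1), treated as a single look with n per arm:

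power = Φ{[Δ√n − z√(2p̄(1−p̄))] / √(p₁(1−p₁) + p₂(1−p₂))}, with Δ = 0.088, p̄ = 0.094, z = 2.00.

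| Loss of 500 | Analysed | Power (5%) | Power (5.1%) |
|---|---|---|---|
| 0% | 500 | 0.917 | 0.910 |
| 4% | 480 | 0.906 | 0.898 |
| 10% | 450 | 0.887 | 0.878 |
| 20% | 400 | 0.848 | 0.837 |

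These figures ignore replacement, which would raise the number analysed.

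**6. Neo-adjuvant therapy.** There are two possible orders. If it is given before randomisation, it is a baseline characteristic and any difference between arms is chance. If it is given after randomisation, it still precedes an intervention that starts 12-24 hours before resection, so a difference is chance or the influence of a known allocation. Neither is an effect of FGS. Section 3.2.2 already has chemotherapy and radiotherapy recorded, but the 7.5 baseline list names only tyrosine kinase inhibitors and immunotherapy.

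**The case against.** The described pathway is short. Discussion at the pre-operative visit precedes consent, and randomisation follows within a week, so randomisation is loosely tied to that visit. Baseline in 7.5 is framed around pre-operative investigations, and 4.1 has the questionnaires completed preoperatively. This stands as a description of the usual patient. It sets no limit, and it does not fit the 3-month budget or the 28-day rule. The section 4 flow chart could not be checked for timing.

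A reader might infer more than the text supports:

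- *Neo-adjuvant patients are randomised three months before surgery.* The protocol permits this but nowhere describes it. No section links the surgical delay to neo-adjuvant therapy, and it could equally cover scheduling of the last recruits.
- *The trial loses power.* The loss figures rest on assumptions, the lower set fits within the allowance, and 7.8 replaces early withdrawals.
- *An outdated stratum or baseline biases the comparison.* A value fixed at randomisation stays balanced in expectation. The cost is precision.
- *Concealment or outcome assessment is compromised.* Allocation is concealed at the moment of randomisation, and histopathology staff are blinded (7.4).
- *The protocol already limits the interval to 28 days.* It does not. That figure triggers re-consent and is counted from consent.

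Section 8.1.3 has the surgeon state the expected margin again after the operation in both arms. That gives a current value, but in the FGS arm it follows the use of fluorescence, so it is not a clean substitute for the stratum. Surgeons are also unblinded whenever randomisation occurs. A shorter gap reduces arm-aware planning without removing it. Finally, the Trial Summary words the therapy objective descriptively, but 3.1.2 and 3.3.2 do not.

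**Conclusion.** The point holds for a delayed subset whose size the protocol does not give and which may include patients having neo-adjuvant therapy. For them, section 7.3 allows the arm to be known up to about three months before resection, on the reading that the budgeted delay runs from recruitment to surgery. The consequences are a route to arm-related loss before the primary outcome exists and less precise adjustment from outdated baseline data. A loss of power is not demonstrated.

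The neo-adjuvant point needs no assumption about timing: it cannot be an effect of FGS and should not be an outcome. Both points lie in the protocol text itself. Later analysis cannot recover a baseline that was not retaken. The change is worth making, though neither point threatens the design.

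**What to change.** 1. Reconcile the Trial Summary with 7.1.2, 7.1.3, 7.2 and 7.3. State in 7.3 that randomisation takes place once a resection date is set, within a stated maximum interval before that date. Twenty-eight days is one example, chosen to match the existing re-consent trigger. State that the margin stratum, tumour data, EQ-5D and TESS are taken at that point, and say what the 3-month delay covers. Early consent may stay.

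   Cost: amendment wording and a prompt in the randomisation system. Sites get less notice to arrange the camera and the ICG visit. Where consent was given early, there is a separate baseline and randomisation step, and re-consent.

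2. Remove neo-adjuvant therapy from the secondary objectives and outcomes (Trial Summary, 3.1.2, 3.2.2, 3.3.2) and list it in 7.5 as a baseline characteristic, available for description and adjustment. Keep adjuvant therapy as an outcome. When the 3.3.2 sentence is split, give adjuvant therapy its own time point, because it cannot be compared on the day of operation.

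   Cost: wording only, since 3.2.2 already has these therapies recorded. This change stands even if the timing of randomisation is left as it is.

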7.4. Blinding

Participants and operating team will not be blinded to the trial intervention due to the requirement for the administration of ICG to the participant and the use of extra technology during the procedure by the operating team. The histopathology staff and senior trial statistician will be blinded and unaware of the surgery type to allow for blinded measurement and analysis of primary outcome. The trial statistician will not be blinded.

7.5. Baseline Assessments & Data

Pre-operative investigations will be as per the treating institution's standard practice but must include biopsy for histological confirmation prior to confirmation of eligibility for the trial. Typically, baseline assessments will also involve local magnetic resonance imaging (MRI) of the primary tumour, as well as computed tomography (CT) scanning of the chest, abdomen, and pelvis to stage the patient. An assessment of fitness for surgery pre-operatively would also be pertinent.

Baseline information will include:

- Age
- Sex at birth
- Treating centre
- Stage of tumour
- Histological subtype
- Tumour size
- Tumour grade
- Tumour depth relative to fascia
- Tumour anatomical location
- Planned operation (limb salvage vs. amputation)
- Concomitant medications specifically tyrosine kinase inhibitors and immunotherapy
- Height and weight
- Ethnicity
- Smoking status
- Diagnosis of diabetes
- Postcode
- EQ-5D-5L/EQ-5D-Y questionnaire
- TESS/pTESS questionnaire

7.6. Trial Assessments

Length of index operation and perceived impact of the intervention on surgical decision making will be collected immediately post-surgery. Follow up visits at 1, 3, 6 and 12 months will follow standard of care follow up clinic visits and will be conducted as per standard of care at the treating centre. These visits will include the completion of questionnaires (EQ-5D-5L/EQ-5D-Y and if applicable TESS/pTESS). At the day of surgery, 1-, 6- and 12-months visits serious adverse events and complications, including extra clinic visits and hospital admissions since previous assessment, will be collected. At day of surgery, 1- and 6 month visits adverse events will be collected. At the 6- month visits, information will be collected on margin status, local/regional/distal recurrence, length of inpatient stay, adverse events, and serious adverse events. At the 12-month visit overall survival will be collected. Surgeon preference for the different methods of surgery will be collected throughout the trial.

SarcoSIGHT

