10.2.2. Analysis of Secondary Outcome Measures

Descriptive analysis will be performed to analyse the nature of the data. Secondary outcomes with binary/multiple measures will be analysed with logistic regression. Survival analysis like the Kaplan-Meier statistic will be used to find the overall survival in each arm. For variables with continuous measure, appropriate regression models will be used. Appropriate Statistical tests depending on the nature of the variables (whether qualitative or quantitative) will be used for comparison between the two treatment arms.

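### Local and regional/distal recurrence are 12-month outcomes, but the protocol names recurrence for collection only at 6 months, so later recurrences are not systematically captured

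*Protocol*

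**What the plan says.** The time point of the outcome is consistent wherever it is stated.

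- The Trial Summary gives the local recurrence measure as "The difference in rate of local recurrence at 12 months" and the regional/distal measure as "The difference in rate of regional/distal recurrence at 12 months".
- Section 3.1.2 introduces the secondary objectives, both kinds of recurrence among them, with "To determine the effect of FGS using ICG compared to the SoC over a 12-month period on the following areas".
- Section 3.3.2 fixes the comparison: "Local/regional/distal recurrence and difference in overall survival will be compared between the two groups at the 12-month time point".

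The collection instructions are in sections 7.6 and 7.7.

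- Section 7.6 names recurrence once: "At the 6- month visits, information will be collected on margin status, local/regional/distal recurrence, length of inpatient stay".
- For the last visit the same section says "At the 12-month visit overall survival will be collected". It also lists events for that visit: "12-months visits serious adverse events and complications, including extra clinic visits and hospital admissions since previous assessment, will be collected". Questionnaires are completed there too. Recurrence is not named.
- In section 7.7 the 12-month column holds EQ-5D, TESS, complications, the SAE check, survival status and cause of death. No row for recurrence can be found at any visit.

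**The concern.** Two prespecified secondary outcomes have no collection instruction at their own time point. A site that follows sections 7.6 and 7.7 to the letter records recurrence status at 6 months and is not asked for it again. The 12-month comparison would then rest on 6-month status, plus whatever later recurrences happen to be reported by another route.

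These outcomes carry weight in this trial. Sections 1.1 and 2 justify reducing unexpected positive margins by their association with more and earlier local recurrence and with poorer survival. Within the funded 12 months of follow-up, recurrence is the most direct evidence on whether a change in margin status reaches the patient. The Trial Summary makes a 5-year time point conditional on further funding, so it cannot be relied on to close the gap.

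**Working it through.** **Step 1. Outcome against collection.** The protocol states no figure to reproduce here; the check is a comparison of sections.

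| Item | Time point | Where |
|---|---|---|
| Local recurrence rate | 12 months | Trial Summary |
| Regional/distal recurrence rate | 12 months | Trial Summary |
| Horizon of secondary objectives | 12 months | 3.1.2 |
| Between-arm comparison of recurrence | 12 months | 3.3.2 |
| Recurrence named for collection | 6 months | 7.6 |
| Recurrence row in the schedule | none found | 7.7 |

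Sections 3.3.2 and 7.6 do not match, and this does not depend on reading the schedule table correctly.

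**Step 2. Could another 12-month item stand in?** Complications, SAEs, extra visits, admissions, survival status and cause of death are all collected at 12 months.

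- The complications listed in section 3.2.2 do not include recurrence. It could enter only as another event that the PI judges to be a complication of surgery.
- Section 8.2.2 does list recurrence as a known risk of surgery, and section 9.2 sends surgery-related adverse events to the complications form. A PI might therefore record it there, but no text requires this.
- A recurrence found at a routine outpatient visit need not meet any seriousness criterion in section 9.1.
- Under section 7.4 the participants and the operating team know the allocation, so discretionary recording could differ between arms.

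These routes give partial capture, not systematic ascertainment.

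**Step 3. Scale, for illustration only.** The protocol gives neither a 12-month recurrence risk nor a hazard shape, so both are assumed. Let r be the 12-month risk and k the Weibull shape:

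- H = -ln(1 - r)
- F(6) = 1 - exp(-H × 0.5^k)
- share of first-year recurrences after month 6 = 1 - F(6)/r

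Worked case, r = 0.10 and k = 1 (constant hazard): H = 0.1054; F(6) = 1 - exp(-0.0527) = 0.0513; share = 1 - 0.0513/0.10 = 0.487. In an arm of 250 the expected number of recurrences is 250 × 0.10 = 25, of which about 250 × (0.10 - 0.0513) = 12 fall after month 6.

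| r | k = 0.8 | k = 1 | k = 1.5 |
|---|---|---|---|
| 5% | 41.9% | 49.4% | 64.1% |
| 10% | 41.3% | 48.7% | 63.4% |
| 15% | 40.6% | 48.0% | 62.8% |
| 20% | 39.9% | 47.2% | 62.1% |
| 30% | 38.3% | 45.6% | 60.5% |

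With a constant hazard the share is close to one half almost by construction, because month 6 is the midpoint of the window. Shape matters more than risk, and the full range is 38.3% to 64.1%. These are shares that fall after the only named collection visit. They equal the share lost only if nothing is captured indirectly.

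**The case against.** The best reply is that the protocol nowhere says recurrence is collected at 6 months only; that is inferred from silence at 12 months. Section 4.1 provides for a 12-month eCRF, the visit coincides with a standard-of-care clinic, section 11.1 makes clinical notes a source document, and the 12-month intent is plain from three other places. The schedule table is also weak evidence. The text available for this review is damaged at the edges, the flow chart in section 4 is not reproduced in it, and the table has no rows for inpatient stay or adjuvant therapy either, so it does not list every outcome. All of this stands, and it limits how much weight the missing row can bear. It does not remove the mismatch between 3.3.2 and 7.6, because section 7.6 goes through the visits item by item and places recurrence at 6 months.

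A reader might infer that every recurrence between 6 and 12 months is lost. The documents do not support that, given the indirect routes in step 2.

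A reader might also infer from section 10.2.2 ("Secondary outcomes with binary/multiple measures will be analysed with logistic regression") that deaths without recurrence are mishandled and that logistic regression must be replaced. The protocol does not support that either. It assigns no method to recurrence by name and says nothing on how such deaths are treated. A binary comparison at a fixed 12 months is legitimate for an outcome defined as a rate, and the handling of competing events is commonly left to the SAP, which is not at hand.

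**Conclusion.** The inconsistency is real. Recurrence is defined and compared at 12 months but named for collection only at 6, so recurrences after month 6 are captured only in part and at the discretion of unblinded sites. The size cannot be derived from the protocol. Under the assumptions above, about half of first-year recurrences fall in the uncovered window with a constant hazard, and about 38-64% over Weibull shapes 0.8-1.5 and 12-month risks of 5-30%. Indirect capture would reduce the actual loss by an unknown amount.

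The consequence is confined to secondary outcomes. The unexpected positive margin rate, its analysis and the sample size are not touched. The point should still be settled in the protocol, because an SAP cannot recover a status or a date that sites were never asked to record.

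**What to change.** Amend section 7.6 so that recurrence is collected at both the 6- and the 12-month visits, and add a recurrence row to the schedule of events in section 7.7 at the same two visits. Record on the existing eCRFs: recurrence yes or no; local, regional or distal; date; and how it was confirmed. Section 3.2.2 already asks for histological confirmation where possible. Check that the flow chart in section 4 agrees. Moving the outcome to 6 months would also remove the contradiction, but it would go against the Trial Summary and sections 3.1.2 and 3.3.2 and shorten the outcome.

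Recording dates leaves the SAP free to use a time-to-event analysis if it so chooses; no change to section 10.2.2 is needed for this point.

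The cost is a few eCRF fields at a visit that already takes place, plus amendment wording, with no new visit or investigation. If some participants have already passed 12 months, their status would have to be taken from clinical notes. That retrieval, over up to 20 sites, grows the longer the change waits.
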